9.3 Participant withdrawal from the trial

Participants may withdraw their consent for the trial at any time. If this occurs, this will be recorded in the CRF using the study completion / discontinuation form, in the trial database and on the trial withdrawal log. However, data collected up to the time of participant's withdrawal will be retained, and used in the final analysis, and this is made clear to the patient at the time of consent.

Participants wishing to withdraw involvement (treatment and / or completion of questionnaires) will be asked to consent to use of data from their medical records.

9.4 Loss to follow-up

Participants will be defined as lost to follow up if they have not been contactable, despite all reasonable efforts, at the point of final data collection (24 months post randomisation). If a participant is lost to follow up, this will be recorded in the CRF using the study completion/discontinuation form. Data about pregnancy outcomes and whether hysteroscopic removal of submucous fibroids or endometrial polyps were removed for participants lost to follow-up will be sought directly from medical notes.

10. Safety Reporting

ICH-GCP requires that both investigators and sponsors follow specific procedures when reporting adverse events in clinical studies. These procedures are described in this section.

10.1 Definitions

Table 3 - Adverse Event and Serious Adverse Event information

Term	Definition
Adverse Event (AE)	Any untoward medical occurrence in a study participant. (refer to SOP PM004 Adverse Events and Serious Adverse Events for more details)
Unexpected AE/SAE	An adverse event or serious adverse event which has not been pre-specified as expected
Serious Adverse Event (SAE)	An AE which is serious, defined as any untoward medical occurrence or effect that: 
● Results in death● Is life-threatening*● Requires hospitalisation or prolongation of existing inpatients' hospitalisation**● Results in persistent or significant disability or incapacity● Is a congenital anomaly/birth defect● Is otherwise considered medically significant by the investigator***
Related AE/SAE	An AE or SAE which is related to a research procedure

*The term life-threatening in the definition of a serious event refers to an event in which the patient is at risk of death at the time of the event; it does not refer to an event that hypothetically might cause death if it were more severe, for example, a silent myocardial infarction.

**Hospitalisation is defined as an inpatient admission, regardless of length of stay, even if the hospitalisation is a precautionary measure for continued observation. Hospitalisations for a pre-existing condition, that has not worsened or for an elective procedure do not constitute an SAE.

***Other important medical events that may not result in death, be life-threatening, or require hospitalisation may be considered a serious adverse event/experience when, based upon appropriate medical judgement, they may jeopardise the patient and may require medical or surgical intervention to prevent one of the outcomes listed in this definition.

10.2 Recording and reporting

AEs and SAEs are defined as an event that occurs after the patient has provided written informed consent for trial entry and up to completion of the 24 month follow-up by the last participant recruited (LPLV).

Hysteroscopic resection of submucous fibroids and endometrial polyps is a routine procedure for which the side effects are understood. Therefore, only those AEs which are deemed serious or of particular relevance to the procedure will be recorded / reported in this trial. These are listed as 'expected AEs' in Table 4.

Adverse Events

Participants will be asked for any details of adverse events, at four time points up to the participants' final study related follow-up event; post procedure (if randomised to receive hysteroscopic resection of submucous fibroids or endometrial polyps), then at 6, 15 and 24 months post randomisation. AEs or SAEs may also be identified by the Research Nurse/Associate PI/Dr, or any other individual, at any point during the study, up to last patient last visit.

When an event is identified the process for recording and reporting outlined in Figure 5 will be followed. The local PI (or other suitably trained member of research staff, if the task is delegated to them) should be notified immediately and assess the event for classification as an SAE (see definition in section 10.1).

AEs confirmed as NOT serious will be checked against the list of expected AEs (Table 4).

Expected AEs

AEs which are expected will be recorded by site staff in the participant CRF.

Unexpected AEs

AEs which are not expected will not be recorded on the basis that hysteroscopic resection of submucous fibroids and endometrial polyps is a routine procedure, for which the side effects are understood. We do not anticipate any AEs, which are of relevance to the intervention, other than those listed in Table 4, unless the site PI considers the events to be significant.

Sites are asked to enter all available information onto the study database as soon as possible after the site becomes aware of the event.

Table 4 - Expected Adverse Events

Gynaecological / obstetric related	Procedure related (immediate)	Procedure related (delayed)

● Placenta accreta, increta, percreta● Placenta abruption● Growth retardation● Foetal distress● Antepartum haemorrhage● Post-partum haemorrhage● Placenta Praevia (grade 3 & 4)● Placental abruption● Manual removal of placenta	
● Uterine perforation● Bowel injury● Bladder injury● Significant bleeding during the procedure resulting in additional intervention● Air embolism (though this is very rare and more commonly associated with resection of Type 2 submucous fibroids)● Fluid overload and hyponatremia● Vasovagal reaction (hypotension and fainting) requiring additional intervention during the procedure (e.g. presence of anaesthetist) OR after the procedure● Return to theatre immediately	
● Post-operative adhesions requiring intervention● Infection

Serious Adverse Events

All AEs classed by the PI or delegate as serious will require more detailed information to be recorded in the participant CRF. In such cases, the event must also be reported to the Sheffield CTRU within 24 hours of the site becoming aware of the event (see section 10.4).

[figure not shown]
Expected Serious Adverse Events

Expected SAEs are those events listed in Table 4 which are assessed as serious using the definition in section 10.1.

Unexpected Serious Adverse Events

All unexpected serious adverse events should be assessed for causality by the PI or delegate. Following reporting of these events within 24 hours by site staff to the CTRU, all unexpected SAEs will be reported by the CTRU to the sponsor and DMEC. SAEs which are unexpected and related / suspected to be related to the intervention will be reported further by the CTRU to the REC within 15 working days.

Figure 5 - Recording and reporting of AEs and SAEs

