In these cases, the trial will be explained to the patient before undergoing hysteroscopy and informed consent taken prior to any study related procedures being performed (**document: ICF**). For the purpose of confirming eligibility for the trial, one other imaging technique will be used either before or during the hysteroscopy, to provide a measurement of the fibroids and/or polyps (examples given in section 5.3.1). If it is confirmed that the patient meets the eligibility criteria, the patient will be randomised during hysteroscopy. If randomised to the intervention arm, the endometrial polyp/submucous fibroid will be resected. If randomised to the control arm, the endometrial polyp/submucous fibroid will **not** be resected and the procedure will cease.

The assessment of eligibility will be undertaken by the principal investigator or another suitably qualified member of the research team, who has received appropriate training and has been approved by the principal investigator as detailed on the delegation of responsibilities log.

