8.3 Secondary outcomes

Clinical outcomes

2. LBR at 24 months post-randomisation;
3. Time from randomisation to live birth (LBR);
4. Time from randomisation to pregnancy;
5. Clinical pregnancy (an observation of viable intrauterine pregnancy with a positive heart pulsation seen on ultrasound at/after 8 weeks gestation); miscarriage (spontaneous pregnancy loss, including pregnancy of unknown location (PUL), prior to 24 weeks gestation); premature labour (labour that happens before the 37th week of pregnancy); multiple birth (multiple live births per mother, e.g. twins or triplets etc.); still birth (delivery of a still born foetus showing no signs of life after 24 weeks gestation); and ectopic pregnancy rates (pregnancy outside the normal uterine cavity);
6. Detail of hysteroscopy received, including: number of hysteroscopic procedures received, duration of time post-surgery abstaining from sexual intercourse, type of resection performed (i.e. use of electrical energy device, morcellation devices and others). This applies to intervention arm only;
7. Patient satisfaction. A questionnaire will be designed with input from our PPI co-applicants and the Jessop Wing - Reproductive Health Research Public Advisory Panel to assess general patient satisfaction with the fertility treatments received since randomisation into the trial. The questionnaire will be sent to intervention arm participants and will concentrate on a) waiting time for treatment, b) satisfaction and tolerability of procedures received, c) thoughts on pre and post procedure information provided, d) psychological support, e) logistical family implications of surgery, f) procedure related anxiety;
8. Details of fertility treatments received, including details of medications received (e.g. clomid) and assisted reproductive techniques received (e.g. type of treatment, fresh or frozen cycle, quality and number of embryos transferred during IVF, IUI or ICSI cycle);

9. Incorrect diagnosis/absence of abnormalities at surgery. Where techniques other than diagnostic hysteroscopy have been used to visualise the endometrial polyp or submucosal fibroid, data will be collected regarding any false diagnoses of endometrial polyps/submucous fibroids;
10. Type of submucous fibroid (type 0, 1, or 2);
11. Number of participants in the control arm who undergo resection.
12. COVID-19 vaccination status (1st, 2nd, booster, approximate date and type of vaccine);

Safety outcomes

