9.1 Study assessments schedule

Data will be collected at the time points listed below. Follow-up time points should be measured from the date of randomisation. A process flow diagram for data collection is provided in Appendix 1.

Eligibility assessment

Potential or fully eligible participants will be identified initially from medical notes and / or a database search. The site is required to follow the procedures used in their usual pathway for diagnosis and measurement of fibroids and polyps (see examples given in section 5.3.1).

Baseline

Following consent and prior to randomisation baseline data will be collected from participants. They will be asked a series of demographic, health resource use and COVID-19 vaccination status questions either in person during a clinic appointment, or by telephone / video call with a member of clinical research site staff. The questions may also be completed online. Data such as fertility markers, previous fertility treatments, type of infertility, miscarriage and detail of uterine abnormalities may be sought from the patient's medical records.

Intervention delivery – Hysteroscopic Resection

- Women randomized to the intervention arm will have the hysteroscopic procedure arranged as per local procedures.
- Following hysteroscopic resection fertility treatment will commence as planned

Directly Post-hysteroscopy (applies to the intervention arm only)

The clinical person performing the hysteroscopy procedure will be asked to complete a series of questions detailing the procedure which will be entered into the trial database. This will include details of the uterine abnormality (including size, grade and any misdiagnoses discovered during/after the procedure), any complications occurring during the procedure, detail of the techniques used (e.g. bipolar or monopolar resectoscopes, hysteroscopic morcellators or scissors or polyp snares), length of procedure and clinical staff involved. The site will also be asked to

record the number of pre- and post-operative appointments related to the intervention. These questions will apply to patients allocated to the intervention arm only.

Participants will be asked to complete:

A) the Patient Satisfaction Questionnaire (Document: Patient Satisfaction Questionnaire), which will ask questions about the patients' experiences of;

- a) Waiting time for treatment
- b) Satisfaction and tolerability of procedures received
- c) Thoughts on pre and post procedure information provided

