The per protocol population for those randomised to receive hysteroscopic removal of submucous fibroids or endometrial polyps is defined as a patient a) attending the clinic for the hysteroscopic excision of submucous fibroids and or endometrial polyps and b) receiving the procedure per protocol (following the sites usual procedures for hysteroscopic removal of submucous fibroids and / or endometrial polyps) within the first six-months post-randomisation. The PP population for those randomised to the control group and not to receive hysteroscopic removal of submucous fibroids or endometrial polyps is defined as a patient a) attending the clinic and b) not undergoing hysteroscopic removal of submucous fibroids or endometrial polyps procedure per protocol within the first six months post-randomisation.

Safety and adverse events

Adverse events including serious adverse events (death; hospitalization (initial or prolonged); disability or permanent damage; other important medical events), will be reported for each randomised group and compared between the two groups using a Fisher's Exact test or Chi-squared test (as appropriate). A 95% confidence interval (CI) for the difference in adverse event rate between the groups will also be calculated.

Sub-group analyses

An exploratory sub-group analysis using multiple logistic regression, with the primary outcome LBR, will look for an interaction between treatment group and the following sub-groups: a) infertility/recurrent miscarriage and b) type of fertility treatment received. A sub-group analysis looking at interaction between treatment group and type of submucous fibroid may be carried out if a sufficient number of control participants undergo diagnostic hysteroscopy, as part of site's usual diagnostic procedures, with fibroid type identified.

Analysis of time to event outcomes

Within the main trial period all women recruited to the trial will be followed up for a minimum of 2 years post-randomisation. Given the study recruitment will take 2.5 years then the first recruited women will have up to 4.5 years follow-up. Women will be censored at the last known date of follow-up if they have not had a live birth/clinical pregnancy.

Intervention waiting times and withdrawal from randomised treatment

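### The prompted post-procedure adverse-event check follows allocation, not the procedure, so controls who have a hysteroscopy have their immediate non-serious complications found later and by a different route

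*Protocol*

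**What the plan says.** **Enquiry schedule.** Protocol 10.2 states: "Participants will be asked for any details of adverse events, at four time points up to the participants' final study related follow-up event". It lists them as "post procedure (if randomised to receive hysteroscopic resection of submucous fibroids or endometrial polyps), then at 6, 15 and 24 months post randomisation". A woman allocated to resection therefore has four enquiries, and a control has three, the first at 6 months.

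**Operator form.** Under 9.1, the person performing the hysteroscopy answers questions that include "any complications occurring during the procedure, detail of the techniques used". The same paragraph closes: "These questions will apply to patients allocated to the intervention arm only". Table 2 puts the post-procedure adverse-event entry in a column marked for the intervention arm only. Section 8.3 restricts the hysteroscopy-detail outcome in the same way: "This applies to intervention arm only".

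**Controls who have a hysteroscopy.** In Pathway 2 (5.3) consent is taken beforehand and, once eligibility is confirmed, "the patient will be randomised during hysteroscopy". For a control the procedure then stops without resection. Sections 6.1 and 9.2 foresee controls choosing resection later, and Table 1 grades how many do so before 6 months.

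**Window and analysis.** Adverse events count from written consent (10.2). The safety population is everyone randomised, and adverse events "will be reported for each randomised group and compared between the two groups using a Fisher's Exact test or Chi-squared test" (11.2), with a 95% confidence interval for the difference.

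**The concern.** The trigger for the prompted check is the allocated arm, whereas the risk of a procedural complication comes from the procedure. Among women who have a hysteroscopy in the trial, those in the intervention arm are asked soon afterwards and the operator is asked directly about complications. Those in the control arm are not.

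The events most exposed are the immediate, non-serious ones in Table 4, such as a vasovagal reaction needing extra help or bleeding needing additional intervention. If some of these go unrecorded in controls, the control rate is too low and the between-arm difference in 11.2 looks larger than it is. Procedure-related complications are part of main-trial objective C (3.2) and a safety outcome (8.3). Because this is a matter of what is collected, analysis cannot repair it afterwards.

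The text also sits uneasily with 9.2, which says that outcome collection carries on in full for women who leave their allocated treatment. Adverse events are one of those outcomes, yet 9.1 and 10.2 leave these women out of the prompted procedural collection.

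**Working it through.** **1. Arm size, from the protocol's own sample size (11.1).** Inputs: 10% v 20% live birth rate, two-sided 5%, 90% power, 5% attrition, 1:1 allocation.

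- n per group = [1.96·√(2·0.15·0.85) + 1.2816·√(0.10·0.90 + 0.20·0.80)]² / 0.10² = (0.990 + 0.641)² / 0.01 ≈ 266, as stated.
- Total 532; 532 / 0.95 = 560, as stated.
- Controls per trial: 560 / 2 = 280.

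The concern does not depend on this calculation, which serves only to fix the 280.

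**2. Schedule side by side.**

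| | Allocated to resection | Control having a hysteroscopy |
|---|---|---|
| Prompted enquiry after the procedure | Yes (10.2) | No |
| Operator asked about complications | Yes (9.1) | No |
| 6-, 15- and 24-month enquiry (Table 2: telephone and medical notes) | Yes | Yes |
| Identification by staff or others at any time (10.2) | Yes | Yes |
| Expedited serious-event reporting (10.2, 10.4) | Yes | Yes |

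Only the first two rows differ.

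**3. Wait until the next scheduled review, at most.**

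- Pathway 2 control: month 0 to month 6 = 6 months.
- Crossover before 6 months: also at most 6 months.
- Resection just after the 6-month contact: 15 − 6 = 9 months.
- Resection just after the 15-month contact: 24 − 15 = 9 months.

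**4. Crossover controls without a prompted check.** Table 1 counts resections before 6 months.

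- Green (under 10%): fewer than 280 × 0.10 = 28.
- Amber (10-50%): 28 to 280 × 0.50 = 140.
- Pathway 2 controls are additional; the protocol gives no number.

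**5. Events occurring.** The immediate complication rate r is an assumption, 2-4%; the protocol gives none.

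- Amber-range crossovers: 28 × 0.02 = 0.56 to 140 × 0.04 = 5.6.
- For scale, 280 intervention procedures: 280 × 0.02 = 5.6 to 280 × 0.04 = 11.2.

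**6. Events missed (illustration).** Let s be the share of control events found by the later routes, assumed 50-80%, and c the crossover share. Assume every intervention woman has the procedure with full detection, and ignore Pathway 2.

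- Missed = 280·c·r·(1 − s): from 0.56 × 0.20 = 0.1 to 5.6 × 0.50 = 2.8 per trial.
- Observed risk ratio / true risk ratio = 1/s: 1/0.8 = 1.25 to 1/0.5 = 2.
- Risk difference: true r(1 − c), observed r(1 − c·s). At r = 4%, c = 50%, s = 50%: 2.0% true, 3.0% observed. At r = 2%, c = 10%, s = 80%: 1.80% true, 1.84% observed.
- At s = 100% nothing is missed and the bias is zero.

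**The case against.** The strongest reply is that controls are not left unobserved. Table 2 schedules both a telephone contact and a notes review for adverse events at 6, 15 and 24 months in both arms. Several immediate Table 4 events are defined by an extra intervention or a return to theatre, so they should leave a clinical record. Pathway 2 women are randomised during the hysteroscopy itself, so trial staff are involved when a complication would occur. Section 10.2 lets anyone identify an event at any time and asks for prompt entry, and serious-event reporting does not depend on arm. All of this stands. A reader might infer that controls are never asked, or that the comparison sets operator reports against memory alone. The schedule supports neither reading. What is missing is a prompt, not a route for capture.

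It can also be said that the restriction was deliberate. The version 2.0 entry in the amendment log removed hysteroscopy detail and patient-cost collection for controls who cross over. That agrees with the current text and is not an error. But the entry does not mention adverse events or complications, nor does it address Pathway 2 controls.

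Section 9.2 partly covers crossovers through its general commitment to keep collecting outcomes, but it does not say how that fits with forms confined to one arm. Figure 5 and the Appendix 1 flow diagram are not available in the text reviewed, so whether they add a prompt cannot be checked.

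**Conclusion.** The point holds as one of unequal timing and method of ascertainment. The prompted check and the complications questions depend on allocation, while Pathway 2 and crossover controls have hysteroscopies inside the same adverse-event window, and the arms are then formally compared. Any resulting bias would under-record procedure harms in controls and exaggerate the between-arm difference. It concerns mainly immediate, non-serious events.

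Its size is uncertain and probably small. Fewer than 28 control resections per trial are affected before 6 months at green-level crossover. The 28 to 140 range is the pilot's amber band, which calls for corrective steps and is not an expected level; 8.2 itself regards control resection within 6 months as unlikely. Two stronger readings should be avoided:

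- The 0.6 to 5.6 events are those that would occur in amber-range crossovers at an assumed 2-4% rate. They are not events lost; only some would be missed, and none if later reviews found them all.
- The 9-month wait does not apply to the 28 to 140 women, who cross over before 6 months and wait at most 6 months. It applies to later resections, which that range does not count.

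The number of Pathway 2 controls is not stated and could raise the total. The primary outcome and the sample size are unaffected. This is a cheap improvement worth making, not a threat to the trial's main conclusion.

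**What to change.** In 10.2, 9.1 and Table 2, make any hysteroscopy performed after consent, in either arm, the trigger for the directly-post-hysteroscopy adverse-event enquiry and for the complications items of the existing operator form. State expressly that this includes Pathway 2 controls and control-arm resections, and reconcile the wording with 9.2. The patient-cost, satisfaction and remaining hysteroscopy-detail items can stay confined to the intervention arm, which keeps the version 2.0 simplification.

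The cost is a short amendment and a few existing questions for the controls concerned. Control-arm resections are already to be counted as a secondary outcome (8.3), so these women are meant to be identified anyway. The downside is minor extra site work, and procedures done at other hospitals will still rely on medical notes.

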5.2 Exclusion criteria

The following exclusion criteria will be applied:

- 1) The presence of additional medical morbidity as a result of the submucous fibroid or endometrial polyp, such as anaemia due to heavy periods or significant pain which necessitates surgical intervention.
- 2) Asherman's syndrome
- 3) Malignancy of endometrial polyp/submucous fibroid is suspected.
- 4) The patient is taking part in any other interventional infertility/fertility trial
- 5) Pregnancy, or pregnancy is suspected.
- 6) Previously randomised into the other HELP Fertility? trial (RCT 1 or RCT2)

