5.4 Informed consent

Resection of submucous fibroids and endometrial polyps is such common practice that site staff and patients may perceive allocation to the control group as a lack of intervention and a detriment to their fertility treatment. Study specific training for staff will be designed to deliver a balanced view of the trial (see section 17.1). A recruitment video, consisting of information from the PIS, will be made available to participants via online platforms (e.g. YouTube) to view at any time prior to or during the consent procedure.

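### For non-serious events, the adverse event list covers harms of resection and pregnancy but no symptom of a retained lesion, so that part of the between-arm comparison tends to favour no resection

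*Protocol*

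**What the plan says.** Protocol section 10.2 sets the scope of safety recording: "only those AEs which are deemed serious or of particular relevance to the procedure will be recorded / reported in this trial". Non-serious events are compared with Table 4. Listed events go into the case report form. For the rest, the rule is that "AEs which are not expected will not be recorded on the basis that hysteroscopic resection" is routine and its side effects are understood. The same paragraph adds that no further events relevant to the intervention are anticipated "other than those listed in Table 4, unless the site PI considers the events to be significant".

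Serious events follow a different rule, with no restriction by arm or cause: "All AEs classed by the PI or delegate as serious will require more detailed information to be recorded in the participant CRF". The definition in section 10.1 includes events that the investigator considers medically significant.

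Exclusion criterion 1 in section 5.2 concerns morbidity resulting from the fibroid or polyp, "such as anaemia due to heavy periods or significant pain which necessitates surgical intervention".

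Section 11.2 (Safety and adverse events) says that adverse events, including serious ones, "will be reported for each randomised group and compared between the two groups" by Fisher's exact or Chi-squared test, with a 95% confidence interval for the difference.

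**The concern.** The reason given for not recording unlisted non-serious events is that the side effects of resection are understood. That reason covers only one arm. Section 5.4 says that "Resection of submucous fibroids and endometrial polyps is such common practice" that staff and patients may see the control allocation as a lack of intervention. The less familiar policy is therefore to leave a diagnosed lesion in place, and the recording rule gives no reason for ignoring its consequences.

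The protocol recognises those consequences at entry, in exclusion criterion 1, but gives them no item during follow-up. A control woman who becomes anaemic and is treated as an outpatient would usually have a non-serious, unlisted event. No defined route takes that event into the data.

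This matters because the recorded events are then tested between arms. If live birth rates turn out similar, the balance of harms will carry weight in choosing between the two policies. A count that includes non-serious harms of one policy and not of the other is a poor basis for that choice. An analysis plan can restrict the test, but it cannot recover events that were never recorded.

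**Working it through.** **Contents of Table 4 (sections 10.2 to 10.3).**

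| Column | Entries | Distinct items | Who can have them |
|---|---|---|---|
| Gynaecological / obstetric | 9 (placental abruption twice) | 8, all pregnancy or delivery | Both arms, if pregnant |
| Procedure, immediate | 8 | 8 | Women who undergo resection |
| Procedure, delayed | 2 | 2 | Women who undergo resection |
| Symptom of a retained lesion | 0 | 0 | Mainly controls |

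Distinct total: 8 + 8 + 2 = 18. Of these, 10 are procedural, 8 obstetric and 0 lesion-related. Section 10.2 also schedules four enquiries in the intervention arm (post procedure, then 6, 15 and 24 months) and three in the control arm.

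**Size of the tilt.** The protocol states no adverse event rate, so there is no figure of its own to reproduce. Let *b* be a recorded background rate common to both arms, *p* the rate of listed procedure events (resection arm only), and *q* the rate of unlisted non-serious lesion events (control arm only). Assume that no woman has more than one kind.

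- Recorded difference (resection minus control): (*b* + *p*) − *b* = *p*
- Difference with lesion events recorded: (*b* + *p*) − (*b* + *q*) = *p* − *q*
- Tilt: *p* − (*p* − *q*) = *q*

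The tilt equals the rate of lesion events lost, whatever the procedure rate. If some resected women also have lesion events, it is the between-arm difference in those events.

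**Illustration, all rates assumed.** There are 280 women per arm (560 per trial, section 11.1) and *b* = 2%. The chance of a significant two-sided Fisher test at 5% is found by exact enumeration.

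| *p* | *q* | Recorded difference | Difference with lesion events | Chance significant, recorded | Chance significant, with lesion events |
|---|---|---|---|---|---|
| 2% | 2% | +2 points | 0 | 21% | 3% |
| 5% | 5% | +5 points | 0 | 79% | 3% |
| 8% | 8% | +8 points | 0 | 98% | 4% |
| 5% | 8% | +5 points | −3 points | 79% | 20% |

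In the first three rows the two policies carry the same overall rate of non-serious harm, but the recorded data show a difference against resection. In the last row the sign is reversed. The recorded procedure events are real harms. The fault is that their counterpart is missing. As *q* approaches zero, so does the tilt.

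**The case against.** Targeted recording is a stated, reasoned choice in a pragmatic trial of a routine procedure, and several safeguards limit the damage.

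- **Serious events.** All are recorded in both arms whatever their cause, under a broad definition. A reader might infer that the whole safety comparison is biased, or that no resection can only look safer. The documents do not support that: the filter acts on non-serious events alone.
- **Investigator provision.** Unlisted events that the site investigator thinks significant may be captured. This stands in part. The clause qualifies what is anticipated and does not clearly instruct sites to record. It refers to relevance to the intervention and relies on staff who know the allocation (section 7.1).
- **Few lost events.** Exclusion criterion 1 removes women whose lesion morbidity already requires surgery, and lesions are limited to 3 cm. This stands: *q* may be low.
- **Omissions on both sides.** Unlisted non-serious pain after resection is dropped too. This also stands and works in the other direction.
- **Monitoring and costs.** A reader might infer that the monitoring committee would see no deterioration in controls, or that the cost comparison inherits the bias. Neither follows. The committee receives recorded adverse events and serious events (sections 10.2 and 10.6), and control women who undergo resection are counted (section 8). Resource use comes from questionnaires in both arms.
- **Extreme contrasts.** A reader might picture procedure events against an empty control column, say 8 v 0 of 280 per arm (3% assumed), with Fisher p = 0.007. That needs no recorded event of any kind among controls, although obstetric and serious events accrue in both arms. With an assumed shared background of 1%, 2% or 5%, the counts become 11 v 3 (p = 0.054), 14 v 6 (p = 0.11) or 22 v 14 (p = 0.23).

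The flow diagram for event recording (Figure 5) is not reproduced in the text available, so it could not be checked.

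**Conclusion.** The point holds for non-serious events. The rule in section 10.2, the contents of Table 4 and the between-arm test in section 11.2 together give a comparison that tends to favour no resection by construction. The direction rests on the protocol's own statement that these lesions can cause anaemia and pain, and on such events being more common where the lesion remains.

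The size cannot be determined from the documents. It equals the between-arm difference in unrecorded lesion events: 2 to 8 points under the assumed rates above, and possibly much less given exclusion criterion 1 and the 3 cm limit. Unlisted post-procedure symptoms offset it by an unknown amount. The comparison of serious events is not affected.

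**What to change.** 1. Add a short lesion-related group to Table 4, recorded identically in both arms at the existing 6, 15 and 24-month contacts and documented in the medical notes: anaemia attributed to uterine bleeding, and pelvic pain or abnormal bleeding leading to treatment or unplanned care.
2. State plainly whether unlisted non-serious events that the site investigator considers significant are to be recorded and, if so, that this applies to both arms.
3. In section 11.2, limit the formal between-arm test to serious events and events collected symmetrically. Report procedure-related events descriptively.

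Do not add histological findings to the new group. Section 6.1 ties histology to the hysteroscopic procedure, so such findings would appear mainly in the resection arm and add to the tilt.

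The cost is a protocol and case report form amendment and slightly more event entry at contacts that already take place. Some reporting bias is possible because the trial is open-label. Requiring documentation in the notes limits it. The change is best made early, because events not recorded during follow-up may be hard to recover.
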